Appendix 1. Schedule of Assessments

Schedule of Assessments – Intravenous Treatment Arm											
Study Phase	Screening ^a		IV Treatment Period								Study Completion ^b
Study Day	D –2 to D–1	D1						D2	D3	D4-D7	
				Post Dose Timepoint							
Study Timepoint	–48 hrs.	Pre-dose ^c	Infusion	10 Min.	0.5 Hr.	1 Hr.	2 Hrs.	8 Hrs.	24 Hrs.	48 Hrs.	
Informed consent	X ^d										
Assent (as required/permitted)	X ^d										
Inclusion/exclusion criteria	X	X									
Medical history/current medical conditions	X										
Demography	X										
Physical examination ^e	X								X		
Height & Weight	X ^f										
Serum or urine pregnancy test ^g	X										
Vital signs (BP & HR) ^h	X	X				X		X	X		
Temperature	X	X							X		
Hematology	X ⁱ								X		
Serum chemistry	X ⁱ								X		

Schedule of Assessments – Intravenous Treatment Arm											
Study Phase	Screening ^a		IV Treatment Period								Study Completion ^b
Study Day	D –2 to D–1	D1						D2	D3	D4-D7	
				Post Dose Timepoint							
Study Timepoint	–48 hrs.	Pre-dose ^c	Infusion	10 Min.	0.5 Hr.	1 Hr.	2 Hrs.	8 Hrs.	24 Hrs.	48 Hrs.	
Study drug administration ^j			X								
PK blood collection		X		X	X	X	X	X	X	X	
Adverse events ^k	< ----- X ----- >										
Prior/concomitant medications ^l	< ----- X ----- >										
		
BMI = body mass index, BP = blood pressure, D = study day, HR = heart rate, ICF = informed consent form, PK = pharmacokinetic
 
^a Screening period of up to 48 hours is permitted.
 
^b Study completion visit may be performed via telehealth with subject's parent/LAR to review ongoing medications and adverse events if the subject is discharged from the hospital before Day 4.
 
^c Pre-dose window is defined as after consent and at least 15 minutes prior to study drug administration.
 
^d Written and signed ICF/assent as applicable must be obtained before any protocol-specific assessment is performed.
 
^e Full physical examination to be performed at Screening and 24 hours post-dose. Symptom-driven physical exams may be performed at other timepoints as necessary.
 
^f Both height and weight to be obtained with shoes off.
 
^g For post-menarchal females of childbearing potential or females who have reached Tanner Stage 3 of breast development only.
 
^h Blood pressure and heart rate to be performed after at least 5 minutes of rest while in supine position.
 
ⁱ Blood samples for hematology and chemistry will be assessed by site's local laboratory. If standard of care laboratory assessments were performed within 24 hours prior to consent/assent, these results may be used for purposes of determining eligibility provided they meet protocol requirements for all screening labs. Refer to Section 8.7.
									

Schedule of Assessments – Intravenous Treatment Arm											
Study Phase	Screening ^a		IV Treatment Period								Study Completion ^b
Study Day	D –2 to D–1	D1						D2	D3	D4-D7	
				Post Dose Timepoint							
Study Timepoint	–48 hrs.	Pre-dose ^c	Infusion	10 Min.	0.5 Hr.	1 Hr.	2 Hrs.	8 Hrs.	24 Hrs.	48 Hrs.	
		^j IV study drug infusion should be administered at room temperature continuously over 30 minutes. ^k Adverse events will be assessed from the time of signing the consent/assent until the study completion visit. ^l All medications taken within 72 hours prior to signing of consent/assent will be collected, in addition to all medications taken during the study.									

Schedule of Assessments – Oral Treatment Arm

Study Phase	Screening ^a	Oral Treatment Period								Study Completion ^b
Study Day	D –2 to D–1	D1						D2	D3	D4-D7
			Post Dose Timepoint							
Study Hour	–48 hrs.	Pre-dose ^c	0	1 Hr.	2 Hrs.	3 Hrs.	8 Hrs.	24 Hrs.	48 Hrs.	
Informed consent	X ^d									
Assent (as required/permitted)	X ^d									
Inclusion/exclusion criteria	X	X								
Medical history/current medical conditions	X									
Demography	X									
Physical examination ^e	X							X		
Height & Weight	X ^f									
Serum or urine pregnancy test ^g	X									
Vital signs (BP & HR) ^h	X	X			X		X	X		
Temperature	X	X						X		
Hematology	X ⁱ							X		
Serum chemistry	X ⁱ							X		
Study drug administration ^j			X							
PK blood collection		X		X	X	X	X	X	X	
Adverse events ^k	< -----X----- >									
Prior/concomitant medications ^l	< -----X----- >									

Schedule of Assessments – Oral Treatment Arm

Study Phase	Screening ^a	Oral Treatment Period							Study Completion ^b
Study Day	D –2 to D–1	D1				D2	D3	D4-D7	
			Post Dose Timepoint						
Study Hour	–48 hrs.	Pre-dose ^c	0	1 Hr.	2 Hrs.	3 Hrs.	8 Hrs.	24 Hrs.	48 Hrs.

BMI = body mass index, BP = blood pressure, D = study day, HR = heart rate, ICF = informed consent form, PK = pharmacokinetic

^a Screening period of up to 48 hours is permitted.

^b Study completion visit may be performed via telehealth with subject's parent/LAR to review ongoing medications and adverse events if the subject is discharged from the hospital before Day 4.

^c Pre-dose window is defined as after consent and at least 15 minutes prior to study drug administration.

^d Written and signed ICF/assent as applicable must be obtained before any protocol-specific assessment is performed.

^e Full physical examination to be performed at Screening and 24 hours post-dose. Symptom-driven physical exams may be performed at other timepoints as necessary.

^f Both height and weight to be obtained with shoes off.

^g For post-menarchal females of childbearing potential only.

^h Blood pressure to be performed in supine position.

ⁱ Blood samples for hematology and chemistry will be assessed by site's local laboratory. If standard of care laboratory assessments were performed within 24 hours prior to consent/assent, these results may be used for purposes of determining provided they meet protocol requirements for all screening labs. Refer to Section 8.7.

^j Oral study drug will be administered to subjects in the morning with no food or drink except water for at least 6 hours prior to dosing. After oral dosing, subjects will have no food or drink except water for at least 2 hours and no dairy products, antacids, or multivitamins for 4 hours.

^k Adverse events will be assessed from the time of signing the consent/assent until the study completion visit.

^l All medications taken within 72 hours prior to signing of consent/assent will be collected, in addition to all medications taken during the study.

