6.2 Inclusion and Exclusion Criteria

Each subject must meet all of the following criteria at Screening and/or Pre-dose to be eligible to participate in the study:

Main Criteria for Inclusion:

1. Written and signed parental/LAR informed consent must be obtained before any protocol specific assessment is performed. Pediatric assent should be obtained in accordance with local hospital and IRB policies.
2. Male and female subjects between 8 and < 18 years of age, inclusive at time of consent/assent.
3. Hospitalized, in stable condition, likely to survive the current illness, and receiving or planned to receive standard of care systemic antibacterial therapy, other than omadacycline, for a suspected or confirmed bacterial infection.
4. Expected to remain hospitalized for at least 2 days following administration of the study drug.
5. Sufficient intravascular access (peripheral or central) for study drug administration (iv treatment only) and blood draws.
6. For subjects who will receive oral study drug only, ability to swallow oral study drug (2 tablets).
7. Weight within the 5th and 95th percentile for age and sex.
8. Females of reproductive potential (post-menarche or has reached Tanner Stage 3 breast development) must have a negative urine or serum pregnancy test and agree to use a highly effective form of birth control (e.g., abstinence, oral contraceptive, intrauterine device, or barrier contraception [e.g., condom]) from Screening through the study completion visit. Males (if sexually active) must agree to use a highly effective method of birth control with female partner(s).
9. Subject and parent/caregiver is willing and able to adhere with the requirements and restrictions of the study.

Main Criteria for Exclusion:

Subjects meeting any of the following criteria at Screening and/or Pre-dose will be excluded from participation in the study:

1. Use of other investigational drugs within 5 half-lives or 30 days prior to Pre-dose, whichever is longer.
2. Evidence or history of a clinically significant medical condition or planned medical intervention that may, in the opinion of the investigator, pose a significant safety risk, impair study participation, or impact the subject's ability to undergo the required study procedures. (Note: Subjects must, in the opinion of the investigator, be physically and mentally competent to participate.)

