7 STUDY TREATMENT(S)

7.1 Treatments Administered

[figure not shown]
Test articles will be supplied by Paratek Pharmaceuticals, Inc. (the sponsor). Test articles will be labeled according to regulations.

The test articles should be administered only to subjects who have provided pediatric assent (as appropriate per local regulations) and informed consent signed by his/her parent/LAR and who meet all of the inclusion criteria and none of the exclusion criteria. Once the test article has been assigned to a subject, it must not be reassigned to another subject.

Following a Screening period of up to 48 hours, eligible subjects will be assigned a dosing regimen of omadacycline per PI discretion.

[figure not shown]

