8.7.3 Pregnancy Assessment

Females of reproductive potential (post-menarchal or has reached Tanner Stage 3 breast development) will have a local laboratory urine or serum pregnancy test at Screening. Results are required for eligibility, retained in source documents, and will be entered in the eCRF. If a positive urine or serum pregnancy test result is obtained during Screening, the subject is not to be enrolled.

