9.1 Screening Phase

The Screening visit should be completed within a 48-hour period prior to enrollment and dosing. The Screening procedures will be used to establish subject eligibility and Baseline characteristics for each subject. Following the signing of an ICF/pediatric assent, the site staff will collect/perform the assessments detailed in [Appendix 1](#).

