9.2 Clinical Laboratory Tests

All laboratory testing will be performed by the local laboratory at each site. The relevant local laboratory results from Screening will be used to assess eligibility as per the inclusion/exclusion criteria.

The following laboratory tests will be performed:

Hematology	Hematocrit, Hemoglobin, Mean cell volume, WBC count, Platelet count, White blood cell differential, Neutrophils, Lymphocytes, Monocytes, Eosinophils, Basophils
Serum Chemistry	Blood glucose, Urea, Creatinine, Sodium, Potassium, Chloride, Bicarbonate, ALT, AST, AP, Total bilirubin, Total protein, Albumin, CK, Calcium, Phosphate, Cholesterol, Uric Acid, GGT, Amylase, Lipase

SARS-CoV-2 Sample	Molecular testing for SARS-CoV-2 will be performed at the local laboratory using an upper respiratory sample (e.g. nasopharyngeal swab or saliva) collected either at Screening or upon current hospital admission. Test results from this sample are not required before a subject is enrolled
Pregnancy Assessment	Females of reproductive potential (post-menarchal or has reached Tanner Stage 3 breast development) will have a local laboratory urine or serum pregnancy test at Screening.

ALT = alanine aminotransferase, AP = alkaline phosphatase, AST = aspartate aminotransferase, CK = creatine phosphokinase, GGT = gamma-glutamyl transpeptidase

The hematology, Serum Chemistry, SARS-CoV-2 sample, and pregnancy assessment tests will be performed at the timepoints indicated in the schedule of events (SOE). The schedule of events can be found in [Section 11](#).

Clinical laboratory test results will be presented in data listings. Actual results and changes from Baseline in clinical hematology and serum chemistry will be summarized by treatment within each cohort ,and time point. Shift from baseline in terms of low/normal/high for hematology and serum chemistry tests, and in terms of normal/abnormal will be summarized by treatment within each cohort and time point.for the safety population.

All laboratory data will be presented in data listings.

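### Oral-arm schedule footnote g leaves pre-menarchal girls at Tanner Stage 3 out of the Screening pregnancy test that inclusion criterion 8 requires

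*Protocol*

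**What the plan says.** The Protocol defines who needs a pregnancy test in several places. Inclusion criterion 8 (Section 6.2, repeated in the Synopsis) reads "Females of reproductive potential (post-menarche or has reached Tanner Stage 3 breast development) must have a negative urine or serum pregnancy test". Section 8.7.3 repeats the group, "Females of reproductive potential (post-menarchal or has reached Tanner Stage 3 breast development) will have a local laboratory urine or serum pregnancy test", and adds "Results are required for eligibility, retained in source documents, and will be entered in the eCRF". Neither text distinguishes the oral from the IV route.

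The two schedules in Protocol Appendix 1 differ from each other. Footnote g of the IV-arm schedule reads "For post-menarchal females of childbearing potential or females who have reached Tanner Stage 3 of breast development only". Footnote g of the oral-arm schedule reads "For post-menarchal females of childbearing potential only".

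In the SAP, Section 9.2 gives the wider group: "Females of reproductive potential (post-menarchal or has reached Tanner Stage 3 breast development) will have a local laboratory urine or serum pregnancy test at Screening". Footnote g in both SAP schedules (IV and oral) carries the same narrow wording as the Protocol's oral-arm footnote.

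Protocol Section 9.1 directs sites to the schedule for Screening: after consent, "the site staff will collect/perform the assessments detailed in" Appendix 1.

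**The concern.** The schedule of assessments is what site staff work from at the bedside, and Section 9.1 sends them there. For oral-arm subjects it gives a narrower rule than the eligibility criterion it is meant to put into practice, and neither document says which text prevails.

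The two schedules also treat the same girl differently. Route is at the investigator's discretion, so a pre-menarchal girl at Tanner Stage 3 has a scheduled test if she is headed for IV dosing and none if she is headed for oral dosing. No reason is given for this difference.

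What is at stake is a required safety check in minors. If the test is omitted, the likely result is an eligibility deviation. If the omission is caught late, there may be some delay within the 48-hour Screening window. If the criteria check fails as well, a girl is dosed untested. Estimation of the PK parameters is not at stake.

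**Working it through.** No arithmetic underlies the point; it is a comparison of texts.

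**Step 1. Set the statements side by side.**

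| Place | Post-menarchal | Pre-menarchal, Tanner Stage 3 reached |
|---|---|---|
| Protocol Synopsis, inclusion criterion 8 | test | test |
| Protocol 6.2, inclusion criterion 8 | test | test |
| Protocol 8.7.3 | test | test |
| Protocol Appendix 1, IV arm, footnote g | test | test |
| **Protocol Appendix 1, oral arm, footnote g** | test | **not scheduled** |
| SAP 9.2 | test | test |
| SAP Appendix 1, IV arm, footnote g | test | not scheduled |
| SAP Appendix 1, oral arm, footnote g | test | not scheduled |

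The wider group appears in five places (four in the Protocol, one in the SAP) and the narrower in three (one in the Protocol, two in the SAP). The Synopsis and Section 6.2 state the same criterion, so the Protocol has three distinct wide statements against one narrow one. Of the three narrow footnotes, only the Protocol's oral-arm footnote directs sites.

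**Step 2. Ask whether the narrow wording can be read as shorthand for the wide one.** It cannot. The word *only* makes it restrictive. The reference to childbearing potential does not bring Tanner Stage 3 girls back in, because the footnote also requires the girl to be post-menarchal.

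**Step 3. Identify who is affected.** Boys are tested under neither wording. Post-menarchal girls are tested under both. Pre-menarchal girls below Tanner Stage 3 are tested under neither. The wordings differ only for pre-menarchal girls who have reached Tanner Stage 3. The planned oral arm is 10 adolescents + 10 children = 20 subjects, and the affected girls are a subset of these. The documents do not give their number.

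**Step 4. Look for other prompts and safeguards.** Section 8.4 lists the components of the Screening physical examination, and breast or Tanner staging is not among them. Exclusion criterion 5 speaks only of post-menarche females. For this group, protection therefore rests on criterion 8 and Section 8.7.3. Two things enforce them: Section 7.1 restricts dosing to subjects "who meet all of the inclusion criteria and none of the exclusion criteria", and the oral schedule lists the inclusion/exclusion check at both Screening and Pre-dose.

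**The case against.** The strongest reply is that the eligibility rules are correct and complete. Criterion 8 applies whatever the route, Section 8.7.3 makes the result an eligibility requirement, and Section 7.1 bars dosing anyone who fails a criterion. The footnote neither forbids the test nor waives the criterion, so a site that tests the girl satisfies every eligibility rule. Untested dosing needs a second, independent error at the criteria check. Section 7.1 also places the choice of route after Screening, so a subject formally has no arm when the pregnancy test falls due. A delayed enrolment is unlikely to amount to much: the subject is in hospital, a local urine or serum test is enough, and re-screening is allowed.

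Most of this stands, and it limits the consequence. The argument from sequence goes only part of the way. The oral schedule has its own Screening column, and inclusion criterion 6 and exclusion criteria 3 and 4 are specific to oral dosing, so the intended route has to be considered during Screening. A site expecting to dose orally has reason to work from the oral schedule then. It is also fair to call this an internal inconsistency rather than a design decision; the intended rule is plain from the other texts. That does not make the footnote harmless, because it is the operational text that is wrong.

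**Conclusion.** The concern holds. Oral-arm footnote g contradicts inclusion criterion 8, Section 8.7.3 and the IV-arm footnote by leaving out pre-menarchal girls who have reached Tanner Stage 3. It should be corrected, but it is not a critical fault, because the governing eligibility text already requires a negative result before dosing.

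The size is small: an unknown subset of 20 planned oral-arm subjects, possibly none. Any harm depends on a site following the schedule rather than the criterion, and untested dosing further depends on the criteria check being missed. The PK and statistical analyses are untouched. The conclusion rests on the current text of both documents and needs no outside figure.

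**What to change.** In Protocol Appendix 1, replace footnote g of the oral-arm schedule with the wording of the IV-arm footnote: "For post-menarchal females of childbearing potential or females who have reached Tanner Stage 3 of breast development only". As housekeeping, make the same change to footnote g in both SAP schedules so that they agree with SAP Section 9.2. Exclusion criterion 5 can stay as it is.

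The cost is one footnote in the next protocol amendment and two in the SAP appendix. No subject has a test that criterion 8 does not already require, and there is no analysis cost.

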eCRF	electronic case report form
HR	heart rate
IV	intravenous
MedDRA	Medical Dictionary for Regulatory Activities
n	number of observations
PK	pharmacokinetic
PT	preferred term
rsq	R squared
SAE	serious adverse event
SAP	statistical analysis plan
SD	standard deviation
SOC	system organ class
T _{1/2}	terminal elimination half-life
TEAE	treatment-emergent adverse event
T _{max}	time to reach maximum observed plasma concentration
V _z	Apparent volume of distribution during the terminal phase

1. Introduction

Omadacycline is an aminomethylcycline, a tetracycline class antibiotic, for intravenous (iv) or oral (po) administration. Intravenous NUZYRA[®] (omadacycline) and oral NUZYRA[®] tablets have been approved by the United States (US) Food and Drug Administration (FDA) for the treatment of adult patients with community-acquired bacterial pneumonia (CABP) and acute bacterial skin and skin structure infections (ABSSSI) caused by susceptible microorganisms.

As omadacycline is active against the causative organisms in potential disease indications such as ABSSSI and CABP, it is reasonable to assume that pediatric exposures comparable to adults will result in similar efficacy outcomes. Therefore, it is necessary to determine the doses required to achieve these exposures. As a class, tetracycline antibiotics do not substantially differ in pharmacokinetics (PK) between adults and children/adolescents.

This study is intended to evaluate the safety, tolerability, and characterize the PK of an intravenous and oral formulation of omadacycline in order to establish pediatric dosing as compared to adult subjects.

This Statistical Analysis Plan (SAP) describes the planned analysis and reporting of the clinical data for Paratek Pharma Protocol PTK0796-PEDPK-20110 (A Phase 1, Open-Label, Multi-Center Study to Evaluate the Safety, Tolerability and Pharmacokinetics of Single Intravenous and Oral Doses of Omadacycline in Pediatric Subjects with Suspected or Confirmed Bacterial Infections).

This SAP is written based on protocol PTK0796-PEDPK-20110, version 4.0, dated 02May2022.

2. Objectives

2.1. Primary Objective

The primary objective of this study is to characterize the PK of single intravenous and oral doses of omadacycline in children and adolescents 8 to < 18 years of age with suspected or confirmed bacterial infections.

2.2. Secondary Objective

The secondary objective is to evaluate the safety and tolerability of single intravenous and oral doses of omadacycline in children 8 to < 18 years of age with suspected or confirmed bacterial infections.

3. Investigational Plan

3.1. Overall Study Description

This is a Phase 1, open-label, multi-center study in children and adolescent subjects (males and females, 8 to < 18 years of age) with suspected or confirmed bacterial infections who are receiving concomitant systemic antibacterial therapy.

This study will consist of 2 age cohorts:

- Cohort 1 (adolescents): 12 to < 18 years of age
- Cohort 2 (children): 8 to < 12 years of age

Subjects will undergo screening evaluations to determine eligibility within 48 hours prior to dosing. Approximately 40 subjects (20 per age cohort) will be enrolled.

On Day 1, per Principal Investigator (PI) discretion, subjects will receive a single dose of either intravenous or oral omadacycline. For those receiving intravenous omadacycline, a 100 mg IV dose (in 100 mL normal saline solution) infused over 30 minutes at room temperature will be administered. For those receiving oral omadacycline, a single dose of 300 mg oral omadacycline tablet (150 mg tablet x 2) will be administered.

Oral study drug will be administered in the morning in a fasted state with no food or drink except for water at least 6 hours prior to dosing. Fasting is defined as no food, antacids, or multivitamins containing multivalent cations (eg, aluminum, magnesium, calcium, bismuth, iron, or zinc) or drink except water for at least 6 hours before dosing. Subjects will have no food or drink except water for at least 2 hours after dosing and no dairy products, antacids, or other aluminium- or calcium-containing products (eg, vitamins, supplements) for 4 hours after dosing.

A total of 7 blood samples for PK analysis of oral omadacycline and 8 blood samples for iv omadacycline will be collected at specified time points prior to dosing and through 48 hours after dosing. Safety assessments will include monitoring of adverse events (AEs), clinical laboratory test results, vital sign measurements, and physical examination findings.

Subjects will complete a Study Completion visit 4 to 7 days after dose completion. This visit may be performed via phone call to subject's parent/legal authorized representative (LAR) to review ongoing medications and adverse events if the subject has already been discharged from the hospital before Day 4.

Refer to the Schedule of Events ([Appendix 1](#)) for the summary of subject visits and assessments through study completion. The planned length of subject participation in the study is up to 9 days.

